### 15.3 NOTIFICATION OF UNANTICIPATED PROBLEM/SERIOUS ADVERSE EVENT/PREGNANCY

**City of Hope Data Coordinating Center  
Department of Clinical Research Information Support**

#### **NOTIFICATION OF UNANTICIPATED PROBLEM/SERIOUS ADVERSE EVENT/PREGNANCY For Use by Participating Institutions Only**

THIS FORM ALONG WITH A COPY OF THE MEDWATCH 3500A FORM MUST BE SUBMITTED TO THE DATA COORDINATING CENTER AT CITY OF HOPE WITHIN 24 HOURS OF KNOWLEDGE OF ONSET OF SERIOUS ADVERSE EVENT, UNANTICIPATED PROBLEM OR KNOWLEDGE OF PREGNANCY (MEETING REPORTING CRITERIA DESCRIBED IN PROTOCOL). SCAN/EMAIL DOCUMENT TO [[contact]](mailto:[contact]) (PLEASE USE #SECURE# IN SUBJECT LINE OF ANY CORRESPONDENCE)

**COH IRB #12267 - Participating Site IRB #** \_\_\_\_\_

#### **Phase I/II trial of MLN9708 plus Pomalidomide and Dexamethasone for Relapsed or Relapsed Refractory Multiple Myeloma**

**Participating/Treating Institution:** \_\_\_\_\_

Reporter: \_\_\_\_\_ Phone #: \_\_\_\_\_

Email: \_\_\_\_\_

**PATIENT INFORMATION Pt Study ID:** \_\_\_\_\_

#### **UNANTICIPATED PROBLEM/SERIOUS ADVERSE EVENT/PREGNANCY INFORMATION**

Serious Adverse Event/Unanticipated Problem: \_\_\_\_\_

Grade: \_\_\_\_\_ Was this a dose limiting toxicity? \_\_\_\_\_

Attribution to MLN9708 (Unrelated, Unlikely, Possible, Probable, or Definite): \_\_\_\_\_

Attribution to Pomalidomide (Unrelated, Unlikely, Possible, Probable, or Definite): \_\_\_\_\_

Start Date of SAE/UP: \_\_\_\_ / \_\_\_\_ / \_\_\_\_

#### **REPORTING INFORMATION**

Has the event been reported to the following?

Via Fax to Data Coordinating Center (COH) \_\_\_\_\_ No \_\_\_\_\_ Yes \_\_\_\_\_ Date: \_\_\_\_ / \_\_\_\_ / \_\_\_\_  
[contact][name]/Email: [[contact]](mailto:[contact]) (use #secure# in subject line)

Participating Site Institutional IRB? \_\_\_\_\_ No \_\_\_\_\_ Yes \_\_\_\_\_ Date: \_\_\_\_ / \_\_\_\_ / \_\_\_\_

**SCAN/EMAIL THIS FORM AND THE MEDWATCH 3500A FORM OR PREGNANCY FORM TO [contact] (USE #SECURE# IN SUBJECT LINE)**

## 15.3.1 Millennium Pregnancy Reporting Form

Pregnancy Form

Page 1 of 2

Report Type:  Initial  Follow-up	Date of Report: _____ / _____ / _____ DD MM Yr
---	---

REPORTER INFORMATION: (Please forward if an alternative physician is more appropriate)	
Reporter name: _____	Title: _____

Address: _____	Telephone No.: _____	Fax No. _____
----------------	----------------------	---------------

City, State/Province: _____	Postal Code: _____	Country: _____
-----------------------------	--------------------	----------------

FATHER'S INFORMATION	
Initials: _____	Date of Birth: _____ / _____ / _____ or Age: _____ years DD MM Yr
Participating in an MPI clinical study?  No  Yes If no, what company product was taken: _____ If yes, please provide: Study drug: _____ Protocol No: _____ Center No: _____ Patient No: _____	
Medical / Familial / Social History (i.e. Include chronic illnesses: specify, familial birth defects/genetic/chromosomal disorders; habitual exposure: specify, alcohol/tobacco; drug exposure: specify, substance abuse and medication use. Please include drug treatment prior to or around the time of conception and/or during pregnancy) _____	Race: _____ Occupation: _____ Number of children: _____

MOTHER'S INFORMATION:	
Initials: _____	Date of Birth: _____ / _____ / _____ or Age: _____ years DD MM Yr
Participating in an MPI clinical study?  No  Yes If no, what company product was taken: _____ If yes, please provide: Study drug: _____ Protocol No: _____ Center No: _____ Patient No: _____	
Medical / Familial / Social History (i.e. Include alcohol/tobacco and substance abuse; complications of past pregnancy, labor/delivery, fetus/baby; illnesses during this pregnancy; assisted conception: specify; other disorders including familial birth defects/genetic/chromosomal disorders; method of diagnosis consanguinity, etc.) _____	Number of previous pregnancies: Full term _____ Pre-term _____ Outcomes of previous pregnancies: (Please indicate number of occurrences) 
 
• Spontaneous abortion: _____
 
• Therapeutic abortion: _____
 
• Elective abortion: _____
 
• Other: _____
 
• Normal live birth: _____
 
• Children born with defects: _____
 
• Stillbirth: _____
 
• Outcome unknown: _____
 

MOTHER'S DRUG EXPOSURE INFORMATION Please include medical prescriptions, vaccinations, medical devices, OTC products, pregnancy supplements (such as folic acid, multivitamins)						
Product Name	Dosage	Route administered to patient	Date of first use (DD/MM/Yr)	Date of end treatment (DD/MM/Yr)	Indication	Contraindicated to pregnancy
			( / / )	( / / )		 Yes  No  Unk
			( / / )	( / / )		 Yes  No  Unk
			( / / )	( / / )		 Yes  No  Unk
			( / / )	( / / )		 Yes  No  Unk

CURRENT PREGNANCY INFORMATION						
Period at exposure: _____ weeks	Trimester	 1	 2	 3	 Unknown	
Date of last menstrual period: _____	DD	MM	Yr			
Pregnancy Status				Fetal/Neonatal Status		
 Pregnancy Ongoing	Estimated date of delivery: _____			 Normal		
 Live Birth	DD	MM	Yr	 Birth defect (structural/chromosomal disorder)*		
 Stillbirth				 Other (non-structural, premature birth, intrauterine death/stillbirth)*		
 Early Termination	 Spontaneous abortion*  Therapeutic abortion*  Elective abortion*  Other*: _____			<small>*If box is checked, please note details in "Additional details" section below</small>		
<small>*If box is checked, please note reason in "Additional Details" section below</small>						
Additional Details:						
Is there evidence of a defect from a prenatal test?  Yes  No						
If yes, indicate which test(s) showed evidence of birth defect:						
 Ultrasound  Amniocentesis  Maternal Serum-Alpha-Fetoprotein  Chorionic Villi Sampling  Human Chorionic Gonadotropin  Other: _____						
Please specify details of defect(s), disorder(s), and/or other anomaly(ies): _____						
What are the defect(s) attributed to: _____						

**Infant Information:**

Gestational weeks at birth or at termination: \_\_\_\_\_ weeks

Date of birth or termination: \_\_\_\_\_ / \_\_\_\_\_ / \_\_\_\_\_  
DD MM YrIf multiple births (e.g. twins), indicate number: \_\_\_\_\_  
(Please complete separate form for each child)

Birth Order (1, 2, 3, etc.) \_\_\_\_\_

Breast-fed:  Yes  No  UnkMethod of delivery:  Normal vaginal  Caesarean section  
 Other: \_\_\_\_\_Sex:  Male  Female  UnkLength: \_\_\_\_\_ cm  inWeight: \_\_\_\_\_ g  lbsHead circumference: \_\_\_\_\_ cm  inApgar score (0-10) at 1 minute: \_\_\_\_\_  UnkApgar score (0-10) at 5 minute: \_\_\_\_\_  UnkResuscitation required:  Yes  No  Unk

Admission to intensive care required:

 Yes  No  Unk**Additional Notes:**

---

---

---

Please attach RELEVANT LABORATORY TESTS AND PROCEDURES (e.g. results of ultrasounds, amniocentesis, chorionic villi sampling, or miscellaneous testing as applicable). In the case of an abnormal evolution or outcome, please send copies of results of all relevant laboratory testing and procedures, including pathology results of products of conception and or autopsy reports if applicable. Please submit any additional relevant information on a separate sheet.

Investigator signature: \_\_\_\_\_

Date: \_\_\_\_\_ / \_\_\_\_\_ / \_\_\_\_\_  
DD MM Yr

Investigator Name: \_\_\_\_\_

## 15.4 International Myeloma Working Group Response Criteria

Response	IMWG criteria
sCR	CR as defined below plus: 
 
normal FLC ratio and
 
absence of clonal cells in bone marrow by immunohistochemistry or 2 – 4 color flow cytometry
 

CR	
 
Negative immunofixation on the serum and urine and
 
disappearance of any soft tissue plasmacytomas and
 
< 5% plasma cells in bone marrow.
 
In patients with only FLC disease, a normal FLC ratio of 0.26–1.65 is required.
 

VGPR	
 
Serum and urine M-protein detectable by immunofixation but not on electrophoresis or
 
≥ 90% reduction in serum M-protein plus urine M-protein level < 100 mg/24 h.
 
In patients with only FLC disease, >90% decrease in the difference between involved and uninvolved FLC levels is required.
 

PR	
 
50% reduction of serum M-protein and reduction in 24 hours urinary M-protein by ≥90% or to < 200 mg/24 h
 
If the serum and urine M-protein are unmeasurable, a ≥ 50% decrease in the difference between involved and uninvolved FLC levels is required in place of the M-protein criteria
 
If serum and urine M-protein are not measurable, and serum free light assay is also not measurable, ≥ 50% reduction in plasma cells is required in place of M-protein, provided baseline bone marrow plasma cell percentage was ≥ 30%
 
In addition to the above listed criteria, if present at baseline, a ≥ 50% reduction in the size of soft tissue plasmacytomas is also required
 

Stable Disease	
 
Not meeting criteria for CR, VGPR, PR or progressive disease
 

MR	
 
25% but < 49% reduction of serum M protein and reduction in 24 hour urine M-
 

	
protein by 50 to 89% which still exceeds 200 mg per 24 hr
 
 
• In addition to the above criteria, if present at baseline, 25-49% reduction in the size of soft tissue plasmacytomas is also required
 
• No increase in size or number of lytic bone lesions (development of compression fracture does not exclude response)
 

Progressive disease	
Increase of <math>\geq 25\%</math> from lowest response value in any one of the following:
 
 
• Serum M-component (the absolute increase must be <math>\geq 0.5 \text{ g/dL}</math>) and/or
 
• Urine M-component (the absolute increase must be <math>\geq 200 \text{ mg/24h}</math>) and/or
 
• Only in patients without measurable serum and urine M-protein, the difference between involved and uninvolved FLC levels. The absolute increase must be <math>> 10 \text{ mg/dL}</math>
 
• Only in patients without measurable serum and urine M-protein and without measurable disease by FLC levels, bone marrow plasma cell percentage (absolute % must be <math>\geq 10\%</math>)
 
• Definite development of new bone lesions or soft tissue plasmacytomas or definite increase in the size of existing bone lesions or soft tissue plasmacytomas
 
• Development of hypercalcemia (corrected serum calcium <math>> 11.5 \text{ mg/dL}</math>) that can be attributed solely to the plasma cell proliferative disorder
 

1. Adapted from Durie BGM, et al. Leukemia 2006; 20: 1467-1473;

All response categories (CR, sCR, VGPR, and PD) require two consecutive assessments made at anytime before the institution of any new therapy; complete response and PR and SD categories also require no known evidence of progressive or new bone lesions if radiographic studies were performed. VGPR and CR categories require serum and urine studies regardless of whether disease at baseline was measurable in serum, urine both or either. Radiographic studies are not required to satisfy these response requirements. Bone marrow assessments need not be confirmed. For progressive disease, serum M-component increases of  $\geq 1 \text{ gm/dL}$  are sufficient to define response if starting M-component is  $\geq 5 \text{ g/dL}$ .

IMWG clarification for coding PD: Clarified that Bone marrow criteria for PD are to be used only in patients without measurable disease by M protein and by FLC levels. Clarified that 25% increase refers to M protein, FLC, and bone marrow results and does not refer to bone lesions, soft tissue plasmacytomas or hypercalcemia. Note the lowest response value does not need to be a confirmed value.

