### **2.2.2 Secondary:**

At the RP2D, for the three drug combination:

2. To characterize and evaluate toxicities, including type, frequency, severity, attribution, time course and duration.
3. To obtain estimates of response duration, depth of response, clinical benefit response, and survival (overall and progression-free).

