## 5. STUDY POPULATION

### 5.1 Inclusion Criteria

Each patient must meet all of the following inclusion criteria to be enrolled in the study:

1. Male or female patients 18 years or older.
2. Voluntary written informed consent must be given before performance of any study related procedure not part of standard medical care, with the understanding that consent may be withdrawn by the patient at any time without prejudice to future medical care.
3. Females of childbearing potential (FCBP) must have a negative serum or urine pregnancy test with a sensitivity of at least 25 mIU/mL within 10 – 14 days prior to and again within 24 hours of starting pomalidomide or MLN9708 and must either commit to continued abstinence from heterosexual intercourse or begin TWO acceptable methods of birth control, one highly effective method and one additional effective method AT THE SAME TIME, at least 28 days before she starts taking pomalidomide or MLN9708 through 90 days after the last dose of study drug. FCBP must also agree to ongoing pregnancy testing. Men must agree to use a latex condom during sexual contact with a FCBP even if they have had a vasectomy from the time of signing the informed consent form through 90 days after the last dose of study drug. All patients must be counseled at a minimum of every 28 days about pregnancy precautions and risks of fetal exposure.
4. All patients enrolled into this trial, must be registered in and must comply with all requirements of the POMALYST REMS™ program.
5. Patients must have a diagnosis of relapsed or relapsed and refractory Multiple Myeloma with a minimum of one prior regimen and a maximum of 5 prior regimens.
6. Patients must have had therapy with a proteasome inhibitor and lenalidomide and be refractory to lenalidomide according to the IMWG definition of refractory disease (progressive disease on or within 60 days of stopping lenalidomide).
7. Patients must have measurable disease defined as one of the following:

- a. Serum M protein  $\geq 0.5$  g/dL
- b. Urine M protein  $\geq 200$  mg/24 hours
- c. Serum free light chain  $\geq 10$  mg/dL provided the FLC ratio is abnormal.

8. Eastern Cooperative Oncology Group (ECOG) performance status 0, 1, or 2.
9. Patients must meet the following clinical laboratory criteria:
  - Absolute neutrophil count (ANC)  $\geq 1,000/\text{mm}^3$

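### As printed, Appendix 15.4 lets only patients with serum M-protein and more than 400 mg/24 h of urine M-protein at baseline reach MR, and does not separate MR from SD, so the MR/SD split may not be reproducible

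*Combined protocol and SAP*

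**What the plan says.** Appendix 15.4 is the only place where the response categories are defined. It is printed twice in the combined document, with the same MR and SD rows. Its relevant parts are:

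- **MR.** The serum fall starts at 25% and must stay below the limit in "49% reduction of serum M protein". It is joined by *and* to a 24-hour urine condition, "protein by 50 to 89% which still exceeds 200 mg per 24 hr". There is no FLC or marrow substitute.
- **PR.** The first line is "50% reduction of serum M-protein and reduction in 24 hours urinary M-protein by" at least 90%, or to below 200 mg/24 h. If neither serum nor urine M-protein is measurable, at least a 50% "decrease in the difference between involved and uninvolved FLC levels is required in place of the M-protein criteria". A marrow substitute follows.
- **SD.** "Not meeting criteria for CR, VGPR, PR or progressive disease". MR is not in that list.
- **Footnote.** "VGPR and CR categories require serum and urine studies regardless of whether disease at baseline was measurable in serum, urine both or either". Nothing comparable is said for MR.

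Section 5.1, item 7, says "Patients must have measurable disease defined as one of the following", and then lists serum M protein, urine M protein and FLC. Note 10 to the Schedule of Events refers to patients whose only measurable disease is in the urine, so such patients are expected.

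Section 2.2.2 sets the secondary objective: "To obtain estimates of response duration, depth of response, clinical benefit response, and survival (overall and progression-free". Sections 3.1 and 10.1.4 count PR or better as overall response and add both MR and SD for clinical benefit. Section 10.1.4 also names depth of response, but does not list its categories.

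**The concern.** The MR row assumes a patient with substantial M-protein in both serum and urine, while eligibility requires only one kind of measurable disease. If the row is applied as written, a minimal response in a patient with one measurable parameter has no route into MR and is recorded as SD. The count of minimal responses would then depend partly on where the disease was measurable and not only on how far it fell.

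The SD row adds a second problem. A patient who does meet MR also meets SD, and the table gives no order of precedence. Sites complete the response forms in a multicenter trial, and I found no central review of response in the documents. Two sites could code identical patients differently.

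At stake is the MR/SD split in any summary of depth of response, which is a named secondary objective.

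**Working it through.** The plan states no figure that depends on the MR row, so there is none to reproduce. The check is to apply the rows literally.

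**1. Baseline urine needed for MR.** For a baseline urine value U and fractional fall r, the residual is U × (1 − r), and it must exceed 200 mg/24 h.

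- At the smallest qualifying fall, r = 0.50: U > 200/0.50 = 400 mg/24 h.
- At the largest, r = 0.89: U > 200/0.11 ≈ 1,818 mg/24 h.

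A patient whose urine is already below 200 mg/24 h cannot qualify. Nor can a patient with no serum M-protein (urine-only or FLC-only). Patients with disease in both who start at 200 to 400 mg/24 h are excluded as well.

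**2. Test patients.** These assume no progression, no plasmacytoma, and a response below VGPR.

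| Baseline disease and change | PR | MR | SD |
|---|---|---|---|
| Serum only, fall 40% | no | no | yes |
| Serum only, fall 49.5% | no | no | yes |
| Serum only, fall 50% | yes | no | no |
| Urine only, 1,000 mg, fall 60% | no | no | yes |
| Both: serum 40%; urine 1,000 mg, fall 60% (400 left) | no | yes | yes |
| Both: serum 40%; urine 350 mg, fall 60% (140 left) | no | no | yes |
| Both: serum 49.5%; urine 1,000 mg, fall 60% | no | no | yes |
| Both: serum 60%; urine 1,000 mg, fall 60% | no | no | yes |
| Both: serum 40%; urine 1,000 mg, fall 92% (80 left) | no | no | yes |

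Three results follow. Only one of the nine patients reaches MR, and that patient also meets SD. No patient is left without a category, because SD is residual. The last two patients do better than MR requires in one parameter and still fall to SD.

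**3. Number of patients.** The documents give no disease-type mix and no rate of minimal response, so these inputs are assumptions: 50% to 90% of the 25 phase II patients have serum-only disease, and 10% to 20% of those have a serum fall in the MR range.

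- Low: 25 × 0.50 × 0.10 = 1.25
- High: 25 × 0.90 × 0.20 = 4.5

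No such patient may occur, so the range is 0 to about 5. Each is worth 1/25 = 4 percentage points.

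**4. Effect on the reported rates.** Take assumed counts of 8 patients at PR or better, 5 true MR and 6 true SD among 25.

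| Moved from MR to SD | MR | SD | Overall response | Clinical benefit |
|---|---|---|---|---|
| 0 | 20% | 24% | 32% | 76% |
| 1 | 16% | 28% | 32% | 76% |
| 3 | 8% | 36% | 32% | 76% |
| 5 | 0% | 44% | 32% | 76% |

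Overall response is 8/25 and clinical benefit is (8 + 5 + 6)/25 throughout. The first counts neither MR nor SD, and the second counts both.

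**The case against.** The best defence is that the rows are shorthand for whatever was measurable at baseline. The footnote demands serum and urine studies regardless of baseline measurability for VGPR and CR only, which suggests that other categories may follow the measurable parameter. The first PR line supports this: it also joins serum and urine with *and*, and its FLC substitute applies only when both are unmeasurable. Read literally, it would shut out a urine-only patient whom eligibility admits. A sensible coder would probably not read either row that way. This is a fair argument about intent, but the appendix does not state the convention. The PR row does at least accept urine below 200 mg/24 h and provides substitutes, and the MR row does neither.

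On the overlap, Sections 3.1 and 10.1.4 list MR and SD as separate categories in descending order, so a coder recording the best category met would choose MR. That is likely, but no rule says so.

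On the gap below 50%, comparison signs before the 25% and 50% may have been lost when the text was extracted, and the plasmacytoma line in the MR row suggests whole-percent bands. Even with an upper limit of 49% inclusive, a fall of more than 49% but less than 50% meets neither MR nor PR. The gap is small. The measurable-disease problem and the SD overlap do not depend on it.

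Finally, Section 10.1.4 specifies no MR-alone or SD-alone rate, and depth among responders (PR or better) is untouched by these rows. That stands, and it limits the consequence.

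**Conclusion.** The point holds for the MR/SD split only. As printed, patients with serum-only, urine-only or FLC-only disease cannot reach MR, and neither can patients with both kinds of disease whose baseline urine is 400 mg/24 h or less. Every MR patient also meets SD. MR is undercounted where such patients occur, and the split may be misclassified and not reproducible across sites. The size is unknown: 0 to about 5 of 25 patients, at 4 percentage points each, under the assumed inputs and the literal reading.

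Four stronger conclusions that a reader might infer are not supported:

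- That a serum fall of 49% to under 50% has no category. The residual SD row captures it, so the fault is placement in SD.
- That the primary endpoint or clinical benefit is affected. The MR and SD rows cannot change either, and no sample-size figure or stopping rule uses MR.
- That a depth-of-response table is certain to be wrong. The plan does not describe such a table, and sites may apply the row sensibly.
- That 1 to 5 patients will be misplaced. That range is a product of assumptions, and zero is possible.

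This is a modest defect in a descriptive secondary objective, worth correcting because the correction is cheap.

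**What to change.** In Appendix 15.4:

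- Apply the MR serum and urine conditions only to the parameter or parameters measurable at baseline.
- State an FLC condition for MR, or say that FLC-only patients are not scored for MR.
- Make the upper limit of MR meet the 50% threshold for PR.
- Add MR to the categories excluded from SD.
- While editing the row, say how to code patients with both kinds of disease whose baseline urine is 200 to 400 mg/24 h, or whose serum and urine falls lie in different bands. The first change alone does not settle these.

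In Section 10.1.4, list the categories to be reported for depth of response.

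The cost is wording in one appendix table and one analysis paragraph, plus the matching response-coding program. The small downside is that the appendix departs from the wording it was adapted from, which a note under the table can record.

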**Appendix 15.5: City of Hope Data Coordinating Center Plan**

**City of Hope  
Data Coordinating Center**

City of Hope has been designated to oversee this trial as the Data Coordinating Center.

This document will serve as guidance as to the responsibilities of the Data Coordinating Center, as well as those of the participating sites.

## **City of Hope Data Coordinating Center Responsibilities**

There are multiple responsibilities associated with serving in the capacity of a data coordinating center. The City of Hope Data Coordinating Center within the Division of Clinical Research Information Support (CRIS) has adequate resources and expertise to carry out these responsibilities:

1. Assist with the design and development of the initial protocol, subsequent amendments and template informed consent documents for use at each participating institution (as applicable).
2. Selecting appropriately qualified participating sites/principal investigators (as applicable).
3. Ascertaining each protocol is reviewed and approved by the IRB at the participating site prior to enrollment of subjects at that site.
4. Ensuring, if the study is federally funded, that each collaborating institution holds an applicable OHRP-approved Federal Wide Assurance (FWA).
5. Collecting and maintaining critical documents for the Trial Master File from participating investigators, e.g. resume/CV, medical license, certification of completion of training (as applicable), laboratory certifications and laboratory norms, financial disclosure forms, etc. Maintaining the file throughout the course of the trial.
6. Distribution of Regulatory Document Binder template to participating sites. A standardized regulatory document template will be sent out to the sites that includes filing of all essential documents for the trial. A standard table of contents and tabbed dividers will be provided to the participating site prior to the protocol initiation meeting.
7. Storing and/or managing data and data and safety monitoring.
8. Protecting the confidentiality of data received from participating sites in accordance with HIPAA.
9. Ensuring informed consent is obtained and documented from each subject in compliance with US regulations.
10. Maintaining documentation of all participating site IRB approvals for the protocol (including all subsequent amendments). Ensuring that participating sites are using the correct version of the protocol and consent document.
11. Assuring that all relevant IRB correspondence (continuing review and amendments) and study status changes are communicated to all participating sites in a timely basis.
12. Providing study specific training to the research personnel at the participating site, both at trial initiation and throughout the course of the trial (re-training as needed). Training will include but not be limited to: protocol background, inclusion/exclusion, registration procedures, treatment schema, dose modification guidelines, AE/SAE/UP reporting guidelines, investigator/staff responsibilities, subsequent amendment changes, etc. The training will be documented and will be continuous throughout the course of the trial.
13. Developing and providing protocol specific case report forms for each participating site (paper and/or EDC). Training of staff on case report forms at study initiation. Continued training of participating site staff if any new changes occur to case report forms during length of study.
14. Centrally registering/randomizing subjects and tracking subject enrollment for all subjects.
15. Tracking, reporting and maintaining documentation of all serious adverse events and

unanticipated problems and dissemination of the information to participating sites for submission to their local committees (as applicable).

16. Providing periodic updates to study sponsor and participating sites on subject enrollment, general study progress, and relevant scientific advances either via email distribution or via teleconferences.
17. Preparation and coordination of teleconferences on an as needed basis (may be weekly, bi-weekly, monthly or quarterly).
18. Primary liaison for participating sites with continuous and frequent communication via email and/or teleconference to ensure protocol is running smoothly, questions have been answered and documenting any issues. Addressing issues with study sponsor immediately.
19. Documenting receipt, shipment and storage of study specimens, drugs and/or devices (if applicable).
20. Conducting continuous quality assurance checks of database, as well as protocol adherence on periodic basis (remote).
21. Monitoring, on a periodic basis, either onsite or remotely of the participating sites to assess research study progress and compliance with the IRB approved protocol.
22. Securing compliance at participating sites that are not adhering to the current version of the research protocol and/or good clinical research practices.
23. Terminating the involvement, if necessary, of non-compliant investigators and reporting such action to the IRB.

